#### • Secondary outcomes:

• To compare the convenience and satisfaction with chemotherapy for patients on standard HDI versus PEG IFN using a chemotherapy convenience and satisfaction questionnaire (CCSQ), with a 30% between-group difference in scores deemed clinically relevant, a mixed randomized-repeated measures ANOVA will be conducted for items CS1 – GP5 as a summation score, since these items share the same Likert scale anchors and valences. Treatment group (HDI versus PEG IFN) will comprise the randomized (betweengroup) factor and treatment period time represents the repeated measures (withingroup) factor. For the repeated measures factor of time, given the different induction phases for the two regimens (i.e., approximately 4 weeks for HDI versus 8 weeks for PEG IFN), the ANOVA will capture outcomes at baseline, 2 weeks, 3 months, 6 months and 12 months, with inclusion of the latter outcome dependent on the amount of missing data.

It should be noted that although the CCSQ is technically an ordinal tool, it will be treated as a continuous/interval scale for the purposes of the ANOVA, with transformation of outcomes as deemed appropriate. It should also be noted that the CCSQ has not been formally validated; therefore, certain items will be presented descriptively, rather than inferentially, as per the judgment of the study authors in keeping with the study's exploratory nature.

Item GF7, which assesses contentment with current quality of life, will be presented descriptively for the two treatment groups as a separate item due to its positively worded valence, at baseline, 2 weeks, 3 months, 6 months and 12 months. No inferential analyses will be conducted for this item.

For item CS10, which assesses satisfaction with current results of chemotherapy, the 3 separate "yes" responses will be collapsed for the sake of convenience and presented descriptively as a dichotomous outcome for the two treatment groups at 2 weeks, 3 months, 6 months and 12 months. No inferential analyses will be conducted for this item.

Items CS11 and CS12, which measure recommendation/choice of chemotherapy regimen, will be presented descriptively for the two treatment groups at 2 weeks, 3 months, 6 months and 12 months. No inferential analyses will be conducted for these items.

Item CS13, which rates the chemotherapy regimen overall, will be presented descriptively for the two treatment groups at the end of the study (i.e., 12 months). No inferential analyses will be conducted for this item.

- To evaluate the treatment-related side effects that may impact the patient's health-related QoL (HRQOL) using the Functional Assessment of Cancer Therapy of Biologic Response Modifier (FACT-BRM), with a 30% between-group difference in scores deemed clinically relevant, a mixed randomized-repeated measures ANOVA will be conducted for all items as a summation score, similar to the analysis plan described for CCSQ items CS1 GP5 (page 23, second bullet point). Separate subscales will be presented descriptively for the two treatment groups.
- The frequency of Grade 3 and 4 toxicities, according to the National Cancer Institute (NCI) Common Toxicity Criteria for Adverse Events (CTCAE) for patients on standard HDI versus PEG IFN, will be presented descriptively for the two treatment groups at 2 weeks, 3 months, 6 months and 12 months. No inferential analyses will be conducted for this outcome.
- Patients' reasons for their choice of treatment with HDI versus PEG IFN, for those cases in which patients are presented with a choice of either treatment option, will be reported descriptively at the study's conclusion (i.e., 12 months). No inferential analyses will be conducted for this outcome.

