# 13 Appendices

# 13.1 Chemotherapy Convenience and Satisfaction Questionnaire (CCSQ)

Below is a list of statements that people receiving chemotherapy like yours have said are important. For each statement, please choose the reply that best fits your experience with receiving chemotherapy, and circle the number corresponding to your reply.

"Chemotherapy" means the drug(s) you receive to treat your cancer or tumor.

	Chemotherapy Experience - 1	Not at all	A little bit	Some- what	Quite a bit	Very Much
CS1	Chemotherapy treatment takes up my time .	0	1	2	3	4
CS2	My chemotherapy treatment takes up my family's time .	0	1	2	3	4
CS3	I worry about side effects from chemotherapy treatment.	0	1	2	3	4
CS4	My chemotherapy treatment causes me physical pain.	0	1	2	3	4
CS5	Receiving chemotherapy is inconvenient.	0	1	2	3	4
CS6	I worry that my chemotherapy will not be effective.	0	1	2	3	4
CS7	Chemotherapy treatment seems harmful to me.	0	1	2	3	4
CS8	My chemotherapy schedule is stressful to me .	0	1	2	3	4
CS9	My chemotherapy schedule is stressful to my family .	0	1	2	3	4
GP5	I am bothered by side effects of treatment.	0	1	2	3	4
	Please answer this last question about how you have felt this past week.					
GF7	I am content with the quality of my life right now.	0	1	2	3	4

Considering your experience with chemotherapy to date, please respond to the following questions.

	Chemotherapy Experience - 2	No, not at all	Yes, to some extent	Yes, for the most part	Yes, completely
CS 10	Are you satisfied with the current results of your chemotherapy?	0	1	2	3

		No	Maybe	Yes
CS 11	Would you recommend this chemotherapy to others with your illness?	0	1	2
CS 12	Would you choose this chemotherapy again?	0	1	2

		Poor	Fair	Good	Very Good	Excellent
CS 13	How would you rate this chemotherapy?	0	1	2	3	4

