Data Analysis -REVISED JULY 2023

Due to the study's pilot study design, sample size was not calculated formally. For both primary and secondary outcomes, descriptive data are presented (i.e., medians and ranges for continuous data, frequencies and percentages for categorical data).

Although the original data plan called for exploratory mixed randomized-repeated measures analysis of variance (ANOVA) to be conducted for the primary and two secondary outcomes, the pattern of missing data across patients at the designated time points was too prevalent (and appeared not to be missing at random) to ensure robust ANOVA results. Therefore, we reported separate non-parametric statistical outcomes when deemed feasible (i.e., adequate and balanced subgroup sample sizes) in an attempt to obtain as much information as possible about data trends and patterns. Because we were unable to capture within-subject correlations over time, as well as the treatment group*time interaction, our results should be interpreted accordingly.

The primary outcome was compliance with HDI and PEG IFN (i.e., percentage of doses taken based on total doses required over 53 weeks, as recorded in patient diaries), with a difference of 30% between groups deemed clinically relevant. We reported frequencies and percentages per week and an overall percentage of doses taken at the end of 53 weeks, with statistical analysis of this outcome.

Secondary outcomes were as follows (with different time points reported depending on the highest outcome frequencies):

- Comparison of the convenience and satisfaction with chemotherapy for patients on standard HDI versus PEG IFN using a chemotherapy convenience and satisfaction questionnaire (CCSQ), summation of items CS1 – GP5, with a 30% between-group difference deemed clinically relevant. Time points of comparison were baseline/week 1, week 3, week 13, week 25, and week 50.
- Item GF7, which assesses contentment with current quality of life, at baseline/week 1, week 3, week 13, week 25, and week 49.
- Item CS10, which assesses satisfaction with current results of chemotherapy, at week 1, week 3, week 13, week 25, week 37, and week 45.
- Items CS11 and CS12, which measure recommendation/choice of chemotherapy regimen, at week 1, week 3, week 13, week 25, week 37, and week 45.
- Item CS13, which rates the chemotherapy regimen overall, at week 1, week 3, week 13, week 25, week 37, and week 45.

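### Merging the three graded yes answers of CCSQ item CS10 removes any arm difference in degree of satisfaction from its summary (a minor reporting point)

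*Protocol*

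**What the plan says.** Protocol Appendix 13.1 prints CS10 as "Are you satisfied with the current results of your chemotherapy", with one no answer (score 0) and three graded yes answers (scores 1 to 3). The lowest yes is "Yes, to some extent" and the highest is "Yes, completely".

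Under the secondary outcomes, Protocol Section 9 says these three yes answers "will be collapsed for the sake of convenience and presented descriptively as a dichotomous outcome for the two treatment groups", at 2 weeks and at 3, 6 and 12 months. It adds: "No inferential analyses will be conducted for this item". Convenience is the only reason given for the merge.

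The analysis that opens the CCSQ part of Section 9 has the aim "To compare the convenience and satisfaction with chemotherapy for patients on standard HDI versus PEG IFN", "with a 30% between-group difference in scores deemed clinically relevant". It uses the sum of items CS1 to GP5, which does not include CS10. CS11 and CS12 (three levels each) and CS13 (five levels) are to be described with no merging.

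The July 2023 SAP lists "Item CS10, which assesses satisfaction with current results of chemotherapy" at weeks 1, 3, 13, 25, 37 and 45. It says categorical data are given as frequencies and percentages. It does not say whether CS10 is shown in two categories or four.

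**The concern.** Satisfaction is named in the secondary objective in the Protocol Synopsis, and Section 6.7 says the CCSQ is there partly to capture it. The summed items ask about time, worry, pain, inconvenience, harm, stress and side effects. CS10 is the one item that uses the word satisfied.

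The merge places the cut at the bottom of the scale. A patient who is satisfied only to a limited degree counts the same as one who is fully satisfied, so the summary separates outright dissatisfaction from everything else. Two arms could look alike on CS10 while differing clearly in how satisfied their patients are.

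The merge also departs from the general rule at the start of Section 9. That rule gives means or medians with spread for ordinal data, and frequencies and percentages for categorical data. Either would keep the grading. Since the Protocol plans no test on CS10, there is no modelling reason to dichotomise.

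**Working it through.** The plan states no rate, effect size or power for CS10, so there is no figure of its own to reproduce. The check is what the merged summary can and cannot show.

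**Inputs from the documents.** Scores 0 to 3 (Appendix 13.1); merge of scores 1, 2 and 3 (Section 9); 100 patients in total with at most a 60:40 split (Sections 9.3 and 3).

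**Inputs assumed.** The response distributions and the exact arm sizes. Several are shown because the documents give none.

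**Step 1: what the merged item measures.** Let p0, p1, p2 and p3 be the proportions at each score in an arm. The merged proportion is p1 + p2 + p3 = 1 − p0. The arm difference (arm 2 minus arm 1) is therefore p0(arm 1) − p0(arm 2). It depends on the no rates alone. If these are equal it is zero, however the yes answers are spread. This needs no assumed rates.

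**Step 2: how much can be lost.** Mean score = 1·p1 + 2·p2 + 3·p3; top two = p2 + p3. The top-two column only gauges the loss and is not a recommended cut.

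| Assumed case | Arm 1, scores 0/1/2/3 (%) | Arm 2, scores 0/1/2/3 (%) | Any yes (%) | Difference (points) | Top two (%) | Difference (points) | Mean score |
|---|---|---|---|---|---|---|---|
| A: large shift, equal no | 10/60/20/10 | 10/20/30/40 | 90 v 90 | 0 | 30 v 70 | 40 | 1.3 v 2.0 |
| B: moderate shift, equal no | 10/45/30/15 | 10/30/30/30 | 90 v 90 | 0 | 45 v 60 | 15 | 1.5 v 1.8 |
| C: no rate also moves | 30/40/20/10 | 10/30/40/20 | 70 v 90 | 20 | 30 v 60 | 30 | 1.1 v 1.7 |
| D: extreme | 0/100/0/0 | 0/0/0/100 | 100 v 100 | 0 | 0 v 100 | 100 | 1.0 v 3.0 |

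Means for case A: 0.6·1 + 0.2·2 + 0.1·3 = 1.3 and 0.2·1 + 0.3·2 + 0.4·3 = 2.0.

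**Step 3: the same loss as information.** A test is used here only as a yardstick, since the Protocol plans none on CS10. Power was simulated with 4,000 runs at two-sided 0.05, using Mann-Whitney on the four levels and Fisher's exact test on yes/no.

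| Case and arm sizes | Four levels | Merged |
|---|---|---|
| A, 50/50 | 96% | 1.5% |
| A, 20/20 | 67% | 1.2% |
| B, 50/50 | 37% | 1.5% |
| C, 50/50 | 90% | 63% |
| C, 20/20 | 52% | 25% |

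In cases A and B the merged item carries nothing about the shift. In case C it keeps part of it. Arm splits of 60/40 and 40/60 give the same pattern.

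**The case against.** The strongest reply is that little rests on CS10.

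- The satisfaction objective is analysed mainly through the CS1 to GP5 sum. That sum carries the 30% relevance margin and was the one planned for repeated-measures ANOVA; the SAP keeps it as the main CCSQ comparison. CS10 has no margin and, in the Protocol, no test. Section 9 also says the CCSQ has not been formally validated and that some items will only be described. This stands.
- CS10 asks about current results, which is narrower than satisfaction with the treatment. CS11 (recommend), CS12 (choose again) and CS13 (overall rating) are graded and not merged, and a large arm difference could well show there too. This stands. A reader might infer that the merge leaves the satisfaction objective without graded data. The documents do not support that.
- The SAP is the later text and does not mention merging. A reader might infer either that the merge was applied or that it was dropped. Neither follows, because what was reported for CS10 cannot be told from the documents.
- Cases A, B and D fix the no rate as equal in both arms, which is exactly the condition for complete masking. Case C shows only partial loss, and nothing in the documents favours one case over another. This stands, so the claim is that the merge can hide a difference, not that it did.
- With about 100 patients and missing data that the SAP calls too prevalent for ANOVA, four levels at six time points will give some thin cells. At 20 per arm, a level chosen by 10% is 2 patients. That is true, but it calls for showing counts beside percentages, and the Protocol does not give sparsity as its reason.

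**Conclusion.** The point holds as a minor improvement. The Section 9 rule makes any arm difference among the three yes levels invisible in the CS10 summary: completely if the no rates are equal, partly if they differ. That follows from the definition of the merged item. Only the size depends on assumed distributions. In the cases with equal no rates, a merged difference of 0 points goes with 15 to 100 points in the top two levels; where the no rate also moves, it is 20 points against 30.

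A stronger conclusion, that the comparison of satisfaction is compromised or that a large difference has been concealed, is not supported. CS10 is one descriptive item in an exploratory pilot, related graded items remain, and no error rate, sample size or decision rule depends on it. The SAP's silence does not remove the rule but leaves its current status unclear.

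**What to change.** In the SAP, state that CS10 is reported as n and % for each of its four levels, by arm, at each listed time point, with the number answering as the denominator. This is the form already open to CS11, CS12 and CS13. Withdraw the Section 9 merging rule in the same place, or say that a yes/no split is shown only in addition to the four levels. No other cut needs to be adopted; the documents support none in particular.

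The cost is two more rows per arm in one descriptive table (four levels instead of two). The questionnaire already records all four levels, so no new data are needed. Some cells at late visits will be sparse, and showing the counts makes that plain.

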#### 6.7.2 FACT-BRM

The FACT-BRM is a questionnaire designed to evaluate HRQOLin cancer patients who are receiving treatment with biologic response modifiers. The FACT-BRM contains 6 domains:

- 1. Physical well-being
- 2. Social/family well-being
- 3. Emotional well-being
- 4. Functional well-being
- 5. Additional concerns Physical
- 6. Additional concerns Mental

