# 13.2 FACT-BRM (Version 4)

#### FACT-BRM (Version 4)

Below is a list of statements that other people with your illness have said are important. Please circle or mark one number per line to indicate your response as it applies to the past 7 days.

	PHYSICAL WELL-BEING	Not at all	A little bit	Some- what	Quite a bit	Very much
GP1	I have a lack of energy	0	1	2	3	4
GP2	I have nausea	0	1	2	3	4
GP3	Because of my physical condition, I have trouble meeting the needs of my family	0	1	2	3	4
GP4	I have pain	0	1	2	3	4
GP5	I am bothered by side effects of treatment	0	1	2	3	4
GP6	I feel ill	0	1	2	3	4
GP7	I am forced to spend time in bed	0	1	2	3	4
	SOCIAL/FAMILY WELL-BEING	Not at all	A little bit	Some- what	Quite a bit	Very much
GS1	I feel close to my friends	0	1	2	3	4
GS2	I get emotional support from my family	0	1	2	3	4
GS3	I get support from my friends	0	1	2	3	4
GS4	My family has accepted my illness	0	1	2	3	4
GS5	I am satisfied with family communication about my illness	0	1	2	3	4
GS6	I feel close to my partner (or the person who is my main support)	0	1	2	3	4
QI	Regardless of your current level of sexual activity, please answer the following question. If you prefer not to answer it, please mark this box and go to the next section.					
GS7	I am satisfied with my sex life	. 0	1	2	3	4

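### The FACT-BRM total is planned as a sum of all items, but the items run in both directions and neither document states reverse-scoring or the direction of the score

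*Protocol*

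**What the plan says.** Protocol Section 9, under the secondary outcomes, plans a repeated-measures ANOVA for the FACT-BRM, "conducted for all items as a summation score, similar to the analysis plan described for CCSQ items" CS1 to GP5. The CCSQ items may be added up, the same section explains, "since these items share the same Likert scale anchors and valences". CCSQ item GF7 is left out of that sum and reported "as a separate item due to its positively worded valence". The CCSQ text also treats the ordinal scale as interval, "with transformation of outcomes as deemed appropriate". For the FACT-BRM the protocol adds: "Separate subscales will be presented descriptively for the two treatment groups".

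Section 6.7.2 says "The FACT-BRM contains 6 domains" and lists them, without scoring. Appendix 13.2 prints the items. The reference list in Section 12 has no scoring source for the instrument.

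The SAP (revised July 2023) drops the ANOVA because of missing data and reports non-parametric results where feasible. It repeats the summation for CCSQ items CS1 to GP5. For the FACT-BRM it mentions only scores, a 30% difference, and comparisons at baseline/week 1 and weeks 3, 13, 25 and 50.

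**The concern.** The protocol itself treats item direction as the condition for adding items. Where a CCSQ item runs the other way, it excludes that item and does not reverse it. It then extends the plan to an instrument whose items point both ways, with no rule for aligning them.

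Taken literally, worse symptoms raise the total, while worse support, coping, appetite, motivation or ability to work lowers it. A treatment that harms patients on both sets of items would have its effect partly cancelled within the total. A reader also cannot tell whether a higher score is the better one. At stake is how the study's FACT-BRM comparison between the two interferon groups can be read. The primary compliance endpoint is not involved.

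**Working it through.** There is no figure in the plan to reproduce. The check counts items by direction and then works out what an unreversed sum does.

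**1. Direction of the items (Appendix 13.2, by wording)**

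| Domain | High is worse | High is better |
|---|---|---|
| Physical | 7 (GP1–GP7) | 0 |
| Social/family | 0 | 7 (GS1–GS7) |
| Emotional | 5 (GE1, GE3–GE6) | 1 (GE2) |
| Functional, legible part | 0 | 1 (GF1) |
| Additional, physical | 6 | 1 (C6) |
| Additional, mental | 5 | 1 (HI6) |
| Total | 23 | 11 |

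By contrast, all ten CCSQ items in the planned sum (CS1–CS9 and GP5) are worse when high.

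The rest of the functional block could not be read in the text available. That is a limit of the text, not of the plan. Assume seven functional items, with GF7 worded as in the CCSQ. The split then lies between 23/17 (the five unread items all positive) and 28/12 (all negative). Both directions are present in every case.

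**2. No reversal is built into the form**

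The items "I am bothered by side effects of treatment" and "I feel close to my friends" carry the same 0–4 codes with the same anchors. The first is coded identically in the CCSQ appendix.

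**3. What the unreversed sum does (34 legible items, maximum 4 × 34 = 136)**

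- Best possible state: 4 × 11 = 44. Worst possible state: 4 × 23 = 92. Spread: 48 points, against 136 once aligned.
- Misordering: a patient who worsens by 1 point on GP5 and by 2 points on GS1 has a total that falls by 1, although both answers got worse. Ranks are taken from the total, so a rank test inherits this order.

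**4. Raw mean shift retained = (negative − positive) / (negative + positive) items that worsen, by one point each**

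- All 34 worsen: (23 − 11)/34 = 12/34 = 35%.
- All except the seven social items: (23 − 4)/27 = 19/27 = 70%.
- Only the negative items: 23/23 = 100%.
- If all items of an assumed 40-item form worsen: (23 − 17)/40 = 15% to (28 − 12)/40 = 40%.

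**5. Standardised shift under equal worsening of the 34 items**

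A sum of mixed items also has a smaller variance when the aligned items correlate. With unit item variance and a common correlation r (assumed; the documents give none):

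- aligned: 34 / √(34(1 − r) + 34²r)
- unreversed: 12 / √(34(1 − r) + 12²r)

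| r | Aligned | Unreversed | Retained | Lost |
|---|---|---|---|---|
| 0.1 | 34/√146.2 = 2.81 | 12/√45.0 = 1.79 | 64% | 36% |
| 0.3 | 34/√370.6 = 1.77 | 12/√67.0 = 1.47 | 83% | 17% |
| 0.5 | 34/√595 = 1.39 | 12/√89 = 1.27 | 91% | 9% |

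**6. Subscales, if left unreversed and all their items worsen equally**

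Physical and social keep 100%, but run in opposite directions to each other. Emotional keeps (5 − 1)/6 = 67%, additional-physical (6 − 1)/7 = 71%, and additional-mental (5 − 1)/6 = 67%.

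**The case against.** The strongest reply is that nothing shows the scores were wrong. The cross-reference to the CCSQ can be read as covering only the ANOVA layout, since much of that text concerns factors and time points. The FACT-BRM is a named, versioned questionnaire with defined domains, and the team may have scored it in an established way. The authors clearly noticed item direction when they set GF7 aside. Printed codes show what a patient circles, not how an answer is later scored. The ANOVA has been abandoned and the SAP does not repeat the summation wording for this instrument. The outcome is secondary, the inference exploratory, and descriptive subscales are promised.

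Much of this stands. A reader might infer that the reported totals were mis-scored; the documents do not show that. A reader might also take 65% (1 − 12/34) as the share of signal lost. That is a raw mean shift under equal worsening of every legible item, social support included. As a standardised loss it holds only if the items are uncorrelated.

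What does not fall away is the omission. On the layout reading the protocol still sums all items without a direction. The transformation clause concerns the use of an ordinal scale in an ANOVA and names no item to reverse. The SAP leaves the score undefined. The subscales help only in part: three of them contain an opposite item, and the SAP does not repeat the commitment to report them.

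**Conclusion.** The concern holds as a scoring rule that is unsafe if followed as written and is not corrected anywhere in either document. That both directions occur on identical codes, and that no reversal or direction is stated, is certain from the text.

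The harm is conditional on items not having been reversed, and its size cannot be fixed from the documents. It depends on which items move and how they correlate. For the legible items the raw shift retained is 35% to 100% across the scenarios shown. The standardised loss under equal worsening is about 9% to 36% for assumed r from 0.5 to 0.1. These are illustrations, not estimates for this trial.

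The point should be fixed, because it decides whether the FACT-BRM comparison can be interpreted. It gives no ground for doubting the primary compliance result.

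**What to change.** In protocol Section 9 and in the SAP, list the FACT-BRM items to be reversed (4 minus the response), so that all items and all subscales run in one stated direction before summing. State that direction and the score range. Either orientation is valid, provided it is named.

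If the reported scores were already aligned, a sentence saying so and naming the reversed items is enough. If they were not, recode the existing responses and re-run the comparisons at baseline/week 1 and weeks 3, 13, 25 and 50, together with the subscale summaries. The cost is a short paragraph and, at most, a recode and re-analysis. No new data are needed.
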